11.3.1 Severity

Severity of AEs will be assessed by the investigator as described in **Appendix B**. AEs not included in the Appendices will be graded for severity using the followings definitions as seen in **Table 7**.

Table 7: AE Severity Grading Definitions

Severity	Definition
Grade 1 (Mild)	No interference with activity, may use one dose of an over the counter medication
Grade 2 (Moderate)	Repeated use of non-narcotic pain reliever > 24 hours or some interference with activity
Grade 3 (Severe)	Activities of daily living limited to <50% of baseline, medical evaluation/therapy required
Grade 4 (Life-Threatening)	Extreme limitation in activity, significant assistance required; immediate medical intervention or therapy required to prevent death
Grade 5	Death

11.3.2 Causality

Causality (likelihood that the event is related to the study agent) will be assessed considering the factors listed under the following categories:

Definitely Related

- reasonable temporal relationship
- follows a known response pattern
- clear evidence to suggest a causal relationship
- there is no alternative etiology

Probably Related

- reasonable temporal relationship
- follows a suspected response pattern (based on similar agents)
- no evidence of a more likely alternative etiology

Possibly Related

- reasonable temporal relationship
- little evidence for a more likely alternative etiology

Unlikely Related

- does not have a reasonable temporal relationship
OR
- good evidence for a more likely alternative etiology

Not Related

- does not have a temporal relationship
OR
- definitely due to an alternative etiology

Note: Other factors will also be considered for each causality category when appropriate. Causality assessment is based on available information at the time of the assessment of the AE. The investigator may revise the causality assessment as additional information becomes available.

The degree of certainty with which an AE can be attributed to administration of the study vaccine will be determined by how well the event can be understood in terms of one or more of the following:

- The event being temporally related with vaccination or reproduced on re-vaccination;
- A reaction of similar nature having previously been observed with this type of vaccine and/or formulation;
- The event having been reported in the literature for similar types of vaccines; and/or
- Whether or not there is another identifiable cause.

All local (injection site) reactions will be considered causally related to vaccination. All malaria cases will be reported as not related to vaccination unless results indicate otherwise.

Asymptomatic parasitemia (positive blood smears without related malaria clinical symptoms) will not be reported as an AE. Clinical malaria will be reported as an AE.

Reports will further classify AEs as follows:

- Related - all AEs that are assessed as definitely, probably, or possibly related.
- Unrelated - all AEs assessed as unlikely or definitely not related.

When reporting to regulatory authorities and IRBs is needed, AE relationship will be determined as noted above.

11.4 Investigator Reporting Responsibilities to the Sponsor

11.4.1 Adverse Events

Line listings, frequency tables and other summary AE data will be submitted to the IND sponsors when needed for periodic safety reviews, review of IND annual reports, review of IND safety reports, and preparation of final study reports.

11.4.3 Unanticipated Problems (UPs)

All UPs that are also adverse events will be reported to the IND sponsor on the NIH Problem Report Form sent by fax or email attachment no later than 7 calendar days of site awareness of the event.

UPs that are not AEs will also be reported to the IND sponsor.

11.4.4 Pregnancy

Pregnancy itself is not an AE. However, complications of pregnancies are AEs and may be SAEs. Pertinent obstetrical information for all pregnancies will be reported to the IND sponsor and LMIV via fax or email within three business days from the site awareness of the pregnancy. Pregnancy outcome data (e.g., delivery outcome, spontaneous, or elective termination of the pregnancy) will be reported to the IND sponsor and LMIV within three business days of the site's awareness of the outcome on a protocol-specified form.

In the event of pregnancy, the following steps will be taken:

- Discontinue the study agent
- Unblind per the site unblinding procedures if the pregnancy occurs within 4 weeks after the last vaccination.
Note: If pregnancy occurs **more than 4 weeks after** the last vaccination, the subject should **ONLY** be unblinded if she meets the criteria for intentional, unscheduled unblinding in **Section 11.4**.
- The subject will be withdrawn from receiving any further investigational products but will continue in follow-up for safety, malaria infection evaluation and modified immunogenicity assays as outlined in **Appendix A**.
- Report to FMPOS EC as an informational item
- Report to NIAID IRB as an informational item
- Report to DSMB, Sponsor Medical Monitor, and Site Medical Monitor
- Advise research subject to notify the obstetrician of participation in the study

11.5 Reporting Procedures to NIAID IRB and FMPOS EC

11.5.1 Reporting to the NIAID IRB

UPs, non-compliance and other reportable events will be reported to the NIH IRB as per Policy 801.

11.5.2 Reporting to the FMPOS EC

Events reported to the NIAID IRB will simultaneously be reported to the FMPOS EC. In addition, SAEs, related or not related to the research will be reported to the FMPOS EC within 72 hours of investigator awareness, regardless of expectedness.

11.6 Additional Investigator Reporting Responsibilities to the Local IRB (NIAID IRB and FMPOS EC)

Investigators are responsible for submitting any IND FDA Safety Reports and UP summaries that are received from the IND sponsor to their local IRB/EC. Investigators must also comply with all local IRB/EC reporting requirements.

11.7 Reporting to the Data and Safety Monitoring Board

As agreed with the Office of Clinical Research Policy and Regulatory Operations (OCRPRO), a DSMB chartered by the IND sponsor, Sanaria, Inc. will be used for this study instead of the NIAID Intramural DSMB.

The DSMB will review the study prior to initiation, after completion of the vaccination series and at study close (as outlined in **Figure 5**). Prior to the administration of the booster

vaccine, the DSMB will review the data from the main phase and the plans for the booster phase. The board may convene additional reviews as necessary, and will issue recommendations concerning continuation, modification, or termination of the study. All SAEs will be reported by the PI to the sponsor immediately upon becoming aware of them. All SAEs that are possibly, probably or definitely related to the study agent, UPs, and safety reports (as available) will be reported by the sponsor to the DSMB.

The DSMB will review the study data to evaluate the safety, efficacy, study progress, and conduct of the study. The sponsor will notify the DSMB of any cases of intentional or unintentional unblinding as soon as possible. The sponsor will notify the DSMB at the time pausing criteria are met and obtain a recommendation concerning continuation, modification, or termination of the study. The PI will submit the written DSMB summary reports with recommendations to the IRB(s).

11.8 Follow-up Adverse Events and Serious Adverse Events

AEs that occur following receipt of a single vaccination are followed until the final outcome is known or until the end of the study follow-up period.

SAEs that have not resolved by the end of the follow-up period will be followed until the final outcome is known. If it is not possible to obtain a final outcome for an SAE (e.g., the subject is lost to follow-up), the reason a final outcome could not be obtained will be recorded by the investigator on the AE CRF (if the CRF is still open) and the SERF.

SAEs that occur after the study follow-up period (six months following the last vaccination) that are reported to and assessed by the Investigator to be possibly, probably, or definitely related must be reported to the study IND sponsor as described above.

11.9 Sponsor's Reporting Responsibilities

SUSARs as defined in 21 CFR 312.32 and determined by the IND sponsor will be reported to FDA and all participating Investigators of related Sanaria trials as IND Safety Reports.

The IND sponsor will also submit an IND Annual Report of the progress of the investigation to the FDA as defined in 21 CFR 312.33.

11.10 Pausing Criteria for the Study

The PI will closely monitor blinded study data as they become available and will make determinations regarding the presence and grading of AEs. The AEs will be evaluated with regard to the known complications associated with administration of vaccine components. If a dose of vaccine is considered unacceptably reactogenic (as described in the following criteria), the study will be paused. No new enrollments and no further vaccinations will be administered by the investigators until reviewed by the DSMB and study IND sponsor. A report of DSMB recommendations will be submitted to the IRBs. The following criteria will be used to define unacceptable reactogenicity of the malaria vaccine (AEs that are possibly, probably, or definitely related to the vaccine will be considered "Related" and will be summarized as such):

1. One or more subjects experience an SAE as defined in **Section 11.4.2** of this protocol that is determined to be possibly, probably, or definitely related to the vaccine or placebo or
2. One or more subjects experience a hypersensitivity reaction (e.g. anaphylaxis, diffuse urticaria) that is probably or definitely related to the vaccine or placebo; or
3. Any severe clinical illness occurs that is not explained by a diagnosis that is unrelated to injection; or

4. Thirty percent of subjects in any dose arm experience the same Grade 2 or higher laboratory abnormality (see **Appendix B**), or Grade 3 systemic AE that is determined to be possibly, probably, or definitely related to the injection (PfSPZ Vaccine or placebo) as defined in this protocol or
5. Ten percent of subjects in any arm experience Grade 3 or higher local reactogenicity; or
6. Any safety issue that the study PI or IND sponsor determines should pause the study.

The IRBs, the NIAID, the FDA, or other government agencies may discontinue the study at any time. Subsequent review of serious, unexpected, and related AEs by the DSMB or IRB, the IND sponsor, the FDA, and other regulatory authorities may also result in suspension of further administration of vaccine at the clinical site (or, in the case of the DSMB, a recommendation to the Sponsor that the study should be suspended). The FDA, other regulatory authorities, and the study sponsor(s) retain the authority to suspend additional enrollment and administration of vaccine for the entire study as applicable.

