3 STUDY DESIGN

This study will enroll healthy Malian adults between 18 and 35 years of age to participate in a randomized double blind, placebo-controlled study to assess the safety, immunogenicity and protective efficacy of boosting during the second transmission season. Participants will be immunized with a 3-dose series of 9×10^5 PfSPZ Vaccine (cryopreserved radiation attenuated *P. falciparum* sporozoites via DVI) at 0, 8 and 16 weeks interval or 0, 1 and 4 weeks starting during the dry season (see [Figure 5](#)). Vaccinated subjects and controls will then be assessed for malaria infection during the ensuing malaria transmission season. Volunteers will be randomized into four arms. Arms 1 and 3a will be randomized first in a 2:1 ratio. Arms 2 and 3b will be randomized into a 2:1 ratio a few weeks later.

At the completion of the follow up phase after the primary series, participants who received all three vaccine doses and are still enrolled in the study will be invited to continue participation in the study to receive a booster vaccine dose. This 4th dose will be administered prior to the beginning of the following transmission season, approximately 10 months post the 3rd vaccination. Those enrolled in the vaccine arms (*Arms 1 and 2*) will receive one injection of 9×10^5 PfSPZ while those participants enrolled in the control arms (*Arms 3a and 3b*) will receive one injection of normal saline. The study will be maintained blinded as the participants transition from the main phase to the booster phase. Vaccinated subjects and controls will then be assessed for malaria infection during the ensuing malaria transmission season.

Figure 5: Study Schema

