4.4 Sample Size and Estimated Duration of the Study

A total of 210 volunteers will be enrolled/randomized in this trial, 70 subjects in each arm vaccine arms (Arm 1 and 2) and 35 subjects in each control arms (Arm 3a and 3b). A total of 140 subjects will receive PfSPZ Vaccine and 70 will only receive placebo.

Definitions for the purpose of this study:

- **Screened** – subjects will receive a study screening number when the informed consent is signed and will either be determined as “eligible” or “screen failure” as noted below.
 - Screening may be completed over the course of multiple visits.
 - Screening, in most cases, will occur within 56 days prior to administration of vaccine #1.
 - If the screening visit is >56 days administration of vaccine #, then an updated medical review and laboratory testing (CBC, ALT, Creatinine, ECG, Urinalysis, Pregnancy test (for females) will be completed to determine eligibility for enrollment.
 - **Note:** HIV, Hepatitis B, Hepatitis C and ECG are to be repeated during booster phase screening **ONLY IF** clinically indicated
- **Eligible** - subjects will be considered eligible to enroll once they have completed the screening procedures and have **met all inclusion** and **not met exclusion** criteria.
- **Screen Failure** – subjects are considered screen failures when they meet one of the following criteria after signing consent:
 - Screening results reveal that the subject is ineligible.
 - Subject withdraws consent before being vaccinated and/or randomized.
 - Subject cannot present to clinic for enrollment prior to study completing enrollment.
 - Subject is determined eligible for enrollment after study completes enrollment.
- **Randomized** – the subjects are considered randomized when they meet the following criteria:
 - Meet eligibility criteria.

- Study identification number (ID) assigned.
- Randomization number assigned.
- **Enrolled** – In the main phase, subject will be considered enrolled beginning with the collection of baseline labs on study Day -14.
 - In the booster phase, subject will be considered enrolled beginning with the receipt of artemether/lumefantrine prior to receiving 4th vaccination
 - Subjects enrolled in main phase but have not received the first vaccination may be replaced up to the accrual ceiling set for the study.
- **Discontinued/Withdrawn** – subjects are considered discontinued when they meet one or more of the following criteria:

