7.2 Assignment of Groups

Enrollment **in the main phase** occurs with collection of baseline study samples on study Day -14. Randomization will occur prior to enrollment, prior to or on study Day -14. Randomization of the subjects in Arm 1 and 3a will occur first as these subjects will be enrolled first. Randomization of Arm 2 and 3b will occur together later prior to enrollment. If a subject was randomized into group 1 or 3a but was not vaccinated, they may be randomized into groups 2 and 3b if still eligible.

If a subject withdraws from the study after randomization, they can be replaced by another subject at random if withdrawal happens prior to receipt of first vaccination. Once a subject has received their first vaccination, they cannot be replaced.

For the booster phase, enrollment will occur at the receipt of the first dose of artemether/lumefantrine prior to vaccination. Enrolled subjects cannot be replaced.

During the study, the list linking randomization numbers to study product (PfSPZ Vaccine or control) will be made available only to the study statistician and associated team members, pharmacy team/syringe preparers (at the start of the study), independent safety monitor (if needed to review as outlined in **Section 11.15.2**), and DSMB chair (if needed for closed session unblinded review). On vaccination days, the vaccines associated with each randomization number will be obtained from the pharmacist.

To ensure proper identification of study subjects, following subject enrollment all subjects will receive an identification card with their photo on it to present at the clinic with each study visit.

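### Pausing criteria 4 and 5 are set per arm, but the blinded data the PI monitors cannot settle whether an arm has reached them, and no available section assigns a count by randomised arm

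*Combined protocol and SAP*

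**What the plan says.** Section 11.10 gives the monitoring task to the PI: "The PI will closely monitor blinded study data as they become available". The PI also decides whether an adverse event is present and grades it. Two of the six pausing criteria are percentages of an arm:

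- Criterion 4 opens with "Thirty percent of subjects in any dose arm experience the same Grade 2 or higher laboratory abnormality" and goes on to related Grade 3 systemic events.
- Criterion 5 reads "Ten percent of subjects in any arm experience Grade 3 or higher local reactogenicity".

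Criteria 1 to 3 need no arm denominator. Criterion 6 is discretionary: "Any safety issue that the study PI or IND sponsor determines should pause the study".

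Under section 11.10.1 the PI or site investigator tells the IND sponsor that a requirement has been met, and the sponsor then tells the DSMB. Section 11.7 has the same order: the DSMB hears once a criterion is met. Its listed reviews fall before the study starts, once the vaccination series is finished, before the booster, and at study close.

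Section 7.2 restricts the allocation list. It "will be made available only to the study statistician and associated team members" and to the pharmacy team and syringe preparers. The independent safety monitor and the DSMB chair have access only if needed.

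Section 4.4 plans "70 subjects in each arm vaccine arms (Arm 1 and 2) and 35 subjects in each control arms (Arm 3a and 3b". Section 3 adds "Arms 1 and 3a will be randomized first in a 2:1 ratio", with Arms 2 and 3b following in the same ratio. Section 3.1 defines four arms, whereas sections 1.7.1 and 1.7.2 (Tables 4 and 5) use 'arm' for the blinded pairs 1/3a and 2/3b.

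**The concern.** A numeric pausing rule exists so that the decision to pause does not depend on someone's impression of the data. Here the number is defined on a unit (Arm 1, 2, 3a or 3b) that the person reporting the breach cannot see. The DSMB's involvement under these rules follows from that report, so it depends on a determination the reporter is not equipped to make. Two investigators could look at the same blinded table and disagree about whether criterion 4 or 5 is met.

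Safety is the primary objective, and up to 200 previously vaccinated participants are to be reconsented for a fourth injection. The rule should work as written for that round.

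**Working it through.** **The plan's own figure.** The only safety probability in the plan is in section 13.2: a 90% chance of at least one adverse event in an arm of 70 at a rate of 0.033. Check: 1 − (1 − 0.033)^70 = 0.9045, so it reproduces. The plan gives no operating characteristics for the pausing criteria.

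**Inputs.** Planned arm sizes are 70 (vaccine) and 35 (control), from section 4.4. Each blinded regimen pair is 70 + 35 = 105. Thresholds are 10% and 30%, from section 11.10.

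**Affected subjects needed, rounded up.**

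| Unit | Criterion 5 (10%) | Criterion 4 (30%) |
|---|---|---|
| Vaccine arm, 70 | 7 | 21 |
| Control arm, 35 | 3.5 → 4 | 10.5 → 11 |
| Blinded pair, 105 | 10.5 → 11 | 31.5 → 32 |

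**Dilution.** With no placebo events, a vaccine arm at threshold shows in the pair as 7/105 = 6.7% or 21/105 = 20.0%, a reduction of one third.

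**If 'arm' means the pair.** The counts become 11 and 32. If all are vaccinees, that is 11/70 = 15.7% and 32/70 = 45.7% of the vaccine arm.

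**Chance of meeting the rule.** Let X ~ Binomial(70, vaccine rate) and Y ~ Binomial(35, placebo rate). Compare P(X ≥ 7) with P(X + Y ≥ 11) for criterion 5, and P(X ≥ 21) with P(X + Y ≥ 32) for criterion 4. Placebo rates are assumptions, shown as a range.

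| Criterion | True vaccine rate | Vaccine arm | Pair, placebo 0 | Pair, placebo 5% (crit. 5) or 10% (crit. 4) |
|---|---|---|---|---|
| 5 | 10% | 0.56 | 0.09 | 0.26 |
| 5 | 15% | 0.92 | 0.48 | 0.70 |
| 5 | 20% | 0.99 | 0.85 | 0.93 |
| 4 | 30% | 0.55 | 0.00 | 0.05 |
| 4 | 40% | 0.97 | 0.20 | 0.50 |
| 4 | 50% | 1.00 | 0.80 | 0.94 |

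**What a blinded count can settle.** Fewer than 7 (or 21) affected subjects in a pair rules out a breach in a full vaccine arm. If control arms count too, the uncertainty starts lower, at 4 (or 11). It ends where no split avoids a breach: at most 6 + 3 = 9 subjects can be affected without some arm meeting criterion 5, and 20 + 10 = 30 for criterion 4. So pooled counts of 4 to 9, or 11 to 30, leave the question open. If the phrase 'dose arm' in criterion 4 means vaccine arms only, the open range is 21 to 20 + 35 = 55.

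**The protocol's own blinded data.** Section 1.7.1 reports 16 Grade 2 neutrophil decreases in pair 1/3a, which is 16/105 = 15.2%. Treating each event as a separate subject, that is at most 16/70 = 22.9% of Arm 1, so this count rules out 30% there. It could be up to 16/35 = 45.7% of Arm 3a, so the raw count does not rule out a breach in the control arm. Only 5 were judged related (at most 5/35 = 14.3%), so neither arm could have met criterion 4 if its relatedness condition covers laboratory abnormalities. The wording leaves that unclear.

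**The case against.** A reader might infer that a vaccine-arm signal at threshold would be invisible, or that the rule could never act at its own threshold. The documents do not support either. The PI sees every event in a pair of known size and 2:1 ratio, the pooled count bounds the vaccine-arm rate, criterion 6 lets the PI or sponsor pause without an arm count, and criteria 1 to 3 are unaffected. All of this stands. It does not make criteria 4 and 5 decidable, because criterion 6 is a matter of judgement.

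A reader might also call the two statements in section 11.10 a flat contradiction. That goes too far: one says what the PI watches, the other sets thresholds. What is missing is the step connecting them. Reading 'arm' as the blinded pair, as sections 1.7.1 and 1.7.2 do, would supply it, but at the cost of the dilution shown above.

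There are unblinded routes. Section 7.2 allows the safety monitor and DSMB chair access if needed. Section 13.1.1 plans vaccine-versus-control comparisons and follow-up of worrying trends on request, and section 11.11 mentions aggregate analysis. None states a duty or timing for counting criteria 4 and 5. The interim analysis in section 13.1.4 concerns efficacy, and unscheduled unblinding in section 11.14 concerns a subject with a serious event.

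Absence is not fully established. Figure 5 (cited for DSMB review timing), section 11.4.2 and the DSMB charter are not in the available text.

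The exposure still to come is limited. The third injections were given in September 2018 (section 1.7), so one injection per subject remains, after a DSMB review of main-phase data. Section 1.7.1 reports only one possibly related Grade 3 event, a platelet decrease. Since section 11.3.2 treats all local reactions as related, no Grade 3 local reaction had been recorded.

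**Conclusion.** The point holds as an operating gap in two of the six pausing criteria. The documents do not show that any threshold was crossed and missed, or that safety signals are hidden from the investigators.

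On the four-arm reading, blinded data leave a range of counts in which nobody assigned to apply the rule can say whether it is met. On the pair reading, the rule can be applied blind but is weaker: at a true vaccine-arm rate of 15% and no placebo events, the chance of meeting criterion 5 falls from 0.92 to 0.48. At 40%, the chance of meeting criterion 4 falls from 0.97 to 0.20. Placebo events narrow the shortfall (to 0.70 and 0.50 at assumed placebo rates of 5% and 10%) but do not remove it. The 15.7% and 45.7% figures are upper limits, reached only with no placebo events and the percentages applied mechanically to the pair.

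These results assume the planned arm sizes and one count per affected subject. Actual numbers in the booster phase will be smaller, and the blinded bounds apply only to full arms. A counting step described only in the material not available would change the conclusion.

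**What to change.** Reconcile sections 7.2, 11.7, 11.10 and 11.10.1, leaving every threshold as it is:

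- State what 'arm' means in criteria 4 and 5. Criterion 4 says 'dose arm' although all vaccinees receive one dose level. State also whether its relatedness condition covers laboratory abnormalities.
- Have the study statistician, who already holds the allocation list, tabulate these two criteria by randomised arm as post-injection data arrive.
- Have the statistician report to the DSMB and sponsor only whether a criterion is met, so that the section 11.10.1 notifications follow while the PI and site stay blinded.
- Have the sponsor state the denominator the criteria intend. None is proposed here, because the choice affects when the study pauses.

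The cost is one paragraph in section 11.10, matching cross-references, and a short recurring unblinded tabulation by someone who is already unblinded.
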